3.2.3.2 Part C

Part C is a randomized, double-blind, parallel-arm adaptive dose exploration study. The goal of Part C is to identify a MCS110 dose lower than 10 mg/kg, which is as efficacious as 10 mg/kg, but may have less side effects. In order to proceed fast, two promising lower doses will be evaluated in parallel, 3 mg/kg and 5 mg/kg of MCS110. Simulations run using prior study information at week 12, log (ratio) of tumor size, and a conservative standard deviation estimate, show that 6 patients per arm in the 3 and 5 mg/kg groups will provide >80% power to declare the lower doses efficacious or not, compared to the 10 mg/kg group.

Once an efficacious lower dose will be identified either 3 mg/kg or 5 mg/kg, the identified arm may be expanded to up to approximately 10 patients for confirmation of safety and efficacy in more patients.

Rationale for assessment schedule C - Adolescent patients

The minimum body weight will be reduced to 30 kg, which is the lower range for children at the age of 12 years.

As per international guidelines for clinical trials in pediatric patients (Howie 2011), the blood volume collected at a time point from a subject 30kg body weight should must not exceed 25 mL per time point, and 50 mL in 8 weeks.

In order to comply with these recommendations only the key safety, PK, PD and Immunogenicity blood samples will be collected and analyzed (see Section 13 Appendix 1: Sample Log, Part C-Adolescent patients).

Risk assessment for effects of MCS110 on adolescent patients is described in the Section 3.5.2.

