Eligibility criteria and safety assessments will be similar as in Part B. Patients will also be followed up to 2 years Corporate Confidential Information or 1.5 years Corporate Confidential Information or 1.5 years every 4 months and they will be offered another treatment course with 10 mg/kg of MCS110 in case of relapse, where relapse is diagnosed at least 6 months after the last MCS110 dose received during the first treatment course (Figure 3-3). Then, the adult and adolescent patients will follow Assessment Schedule Part C re-dosing.

Efficacy assessments will include tumor volume reduction,

, joint-specific questionnaires, VAS and time to relapse.

Conditions of lower dose arm recruitment extension

If a lower dose is identified with at least the same efficacy as 10 mg/kg, defined as tumor volume reduction evaluated by MRI of at least 45%, additional patients may be enrolled in this lower dose group to extend the arm up to approximately 10 patients. Only one dose level, either 3 or 5 mg/kg may be extended and the additional patients will be allocated to the selected dose level in an open label fashion with the same Assessment schedule Part C applied, Corporate Confidential Information

[figure not shown]
[figure not shown]

Figure 3-4 Study design Part C – adults and adolescent (Amendment 7)

Figure 3-5 Study design Part C – adults and adolescents (Amendment 6)

As some patients will have followed study design of Amendment 6 we keep it in the protocol.

Confidential

The planned enrollment number in Part C is approximately 15 patients. If a lower dose is identified to be, at least, as efficacious as 10 mg/kg, additional patients may be enrolled in open label to extend the efficacious 3 mg/kg or 5 mg/kg arm to approximately 10 patients.

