5.2.3 Part C

Approx. 15 patients (including adults and adolescents $\geq 12 - \langle 18 \rangle$ years old) will be randomized in double-blind manner to one of the following 3 parallel arms: 3 mg/kg or 5 mg/kg or 10 mg/kg of MCS110 in a ratio of approximately 2:2:1.

In case a lower dose is identified to be at least as efficacious as 10 mg/kg after 3 doses, additional 4 patients may be enrolled in this lower dose group and randomized in an open label fashion to a total of approximately 10 patients.

Table 5-1 Treatment arms in Part C

Treatment	Double-blind	Potential open label extension
3 mg/kg	n ~6	n ~4*
5 mg/kg	n ~6	n ~4*
10 mg/kg	n ~ 3	n=0

*Either 3 or 5 mg/kg may be expanded.

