Given these scenarios, the table below (Table 9-1) summarizes the power of the study obtained by simulations of 800 trials with 4 different sample sizes.

N patients	Scenario 1	Scenario 2	Scenario 3
12	95%	89%	82%
9	90%	85%	79%
6	88%	83%	74%
3	69%	62%	46%

 Table 9-1
 Power estimates for different scenarios

In scenario 1, with 12 patients and assuming a twofold reduction from baseline in tumor size in the MCS110 group as compared to the placebo group, there is about 95% power to reach the PoC criteria as defined above in the analysis section. With 6 patients (4:2), the power is about 88%.

In Scenario 1, the probability to declare a positive PoC when there is no treatment difference is less than 0.6% at each analysis. Therefore the overall type 1 error rate is bounded at 6% (maximum of 10 analyses). In Scenario 2, the overall type 1 error rate is bounded at 9% and in Scenario 3 bounded at 35%.

Part B

There are anticipated to be about 12 patients in Part B (18 in total for this trial). The following table (Table 9-2) presents the 95% Confidence Interval (CI) for the true proportion of patients with complete tumor response, assuming different proportions of patients with complete tumor response are observed.

response							
\hat{p}^{\star}	0/12 (0)	1/12 (0.08)	2/12 (0.17)	3/12 (0.25)	4/12 (0.33)	5/12 (0.42)	6/12 (0.5)
95% CI	(0, 0.22)	(0.002, 0.38)	(0.02, 0.48)	(0.05, 0.57)	(0.1, 0.65)	(0.15, 0.72)	(0.21, 0 .79)

Table 9-295 percent confidence intervals for the proportion of complete
response

p	7/12 (0.58)	8/12 (0.67)	9/12 (0.75)	10/12 (0.83)	11/12 (0.92)	12/12 (1.00)
95% Cl	(0.28, 0.85)	(0.35, 0.90)	(0.43, 0.95)	(0.52, 0.98)	(0.62, 1)	(0.78, 1)

*Note: \hat{p} is the observed proportion of patients with complete tumor response. The proportion is also converted into two decimal places shown in the parenthesis.

Part C

There are anticipated to be 19 patients in Part C (approximately 37 patients in total for the trial). Simulations run using prior study information, log (ratio) of tumor size, and a conservative standard deviation estimate, show that 6 patients per arm in the 3 and 5 mg/kg groups will provide >80% power to declare the lower doses efficacious or not, compared to the 10 mg/kg group.

Confidential

9.14 **Power for analysis of key secondary variables**

Not applicable.

Corporate Confidential Information

10 Ethical considerations

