7.1.2 Supportive analyses

Part A, Part B and Part C pooled for weeks 1 to 4 (Part A*)

As a supportive analysis, log ratio to baseline of tumor volume at week 4 may be subjected to an Analysis of Covariance (ANCOVA) model. The model will include log transformed tumor volume at baseline and a factor for treatment. Point estimates and 95% confidence interval will be calculated for MCS110 and Placebo separately, and for the difference of means between MCS110 and Placebo. Results will then be transformed back to the original scale.

Part B*:

To study the time course of tumor volume reduction from baseline, a repeated measures ANCOVA model on log ratio to baseline will be fit by resetting the tumor volume at week 4 as baseline for patients in treatment group 2 and the visit number will be adjusted accordingly. The model will include log tumor volume at baseline and visit as fixed effects. Standard fit statistics will be used to determine the best variance-covariance structure. Point estimates and 95% confidence interval will be calculated at each visit. Baseline adjusted tumor volume (+/- SE) over time will be plotted.

Part C:

As a supportive analysis, log ratio to baseline of tumor volume at week 4 may be subjected to an Analysis of Covariance (ANCOVA) model. The model will include log transformed tumor volume at baseline and a factor for treatment. Point estimates and 95% confidence interval will be calculated for each treatment arm and for the difference of means between treatment groups. Results will then be transformed back to the original scale.

The statistical analysis will also be provided by age group (<18 years and ≥18 years).

Parts A, B and C :

A dose-time-response model (Lange and Schmidli 2015) will be used to analyze tumor response data (log ratio to baseline of tumor volume) from Parts A, B, and C. The following equation will be used for the latent concentration $C(t)$ of a patient who receives K doses with dose D_k received at time t_k , $k=1, \dots, K$:

$$C(t) = \sum_{k=1}^q \frac{D_k \theta_1}{\theta_1 - \theta_2} \left\{ \exp \left[-\theta_2 \left(t - \sum_{j=0}^{k-1} \delta_j \right) \right] - \exp \left[-\theta_1 \left(t - \sum_{j=0}^{k-1} \delta_j \right) \right] \right\}$$

where $\delta_0=t_1$, $\delta_j=t_{j+1} - t_j$ for $j=1, \dots, K-1$ and $q \in \{1, \dots, K - 1\}$ is such that $t_q < t \leq t_{q+1}$ and $q=K$ if $t > t_K$.

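### If a lower-dose arm is extended, the plan counts the new patients with those whose week-12 result triggered the extension; the pooled reduction then tends to overstate the dose and is not confirmation

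*Protocol*

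**What the plan says.** Protocol 5.2.3 randomises about 15 Part C patients to 3, 5 or 10 mg/kg "in a ratio of approximately 2:2:1", that is about 6, 6 and 3. Protocol 3.2.2 ties the extension to efficacy equal to 10 mg/kg, "defined as tumor volume reduction evaluated by MRI of at least 45%, additional patients may be enrolled in this lower dose group". Only one dose may be extended, and "the additional patients will be allocated to the selected dose level in an open label fashion". Protocol 5.2.3 words this differently: "additional 4 patients may be enrolled in this lower dose group and randomized in an open label fashion". Protocol 3.2.3.2 gives the purpose: "the identified arm may be expanded to up to approximately 10 patients for confirmation of safety and efficacy in more patients".

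On analysis:

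- **Dose-time-response model** (Protocol 9.4.4, SAP 7.1.2): the patient count lists 6 on each lower dose, rising to 10 for the dose found efficacious. Here the pooling is explicit.
- **Part C summaries** (SAP 7.1): by treatment arm. Patients who switch to 10 mg/kg after three doses form their own groups 4 and 5 for the whole study.
- **Part B\* summaries** (SAP 7.1): switchers stay in their original group for the first three doses.
- **Week-4 ANCOVA for Part C** (SAP 7.1.2): optional, with estimates "for each treatment arm and for the difference of means between treatment groups".
- **Bayesian comparison of 3 and 5 mg/kg with 10 mg/kg** (SAP 7.1): uses data from Parts A, B and C pooled for weeks 1 to 4.

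No readable passage, including the analysis sets in Protocol 9.1 and SAP 5, separates the extension patients.

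**The concern.** The arm is extended because its own first patients did well. Part of that result is chance in the favourable direction, and it stays in the estimate when the same patients are counted again. The new patients dilute it but do not remove it. A result described as confirmation should come from data that played no part in choosing the dose.

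The extension patients are also enrolled later, know their dose and have only one dose open to them. They are not randomised between doses, whatever Protocol 5.2.3 calls it. A by-arm comparison that includes them mixes randomised and non-randomised patients.

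At stake is how well a reader can judge the size of the lower dose's effect. A dose whose true reduction falls short of 45% could be reported, on average, as reaching it.

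**Working it through.** **The plan's own figures.** The counts reproduce: 6 + 6 + 3 = 15, 15 + 4 = 19, and 18 + 19 = 37. The power statement, "6 patients per arm in the 3 and 5 mg/kg groups will provide >80% power", cannot be reproduced, because its SD, effect size and decision rule are not given. Nothing below depends on it.

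**Inputs**

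- First stage n = 6, extension n = 4 (Protocol Table 5-1).
- Trigger: 45% reduction, a log ratio of log(0.55) = -0.598 (Protocol 3.2.2).
- Assumed: the trigger is applied to the mean log ratio of the first 6, and log ratios are normal.
- Assumed SD σ: 0.2, 0.283, 0.424. Protocol 9.13 gives 0.1, 0.2 and 0.3 times √2 (0.141, 0.283, 0.424) for Part A, as residual errors with identical effects in all patients. The value 0.2 is an intermediate choice with no source in the documents.

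**Formula.** For true reduction r, let μ = log(1 - r), SE = σ/√6 and z = (log 0.55 - μ)/SE.

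- P(extend) = Φ(z).
- Mean log ratio of the first 6, given extension: μ - SE·φ(z)/Φ(z).
- The extension patients carry no selection, so the pooled 10 keep 6/10 of that shift: μ - 0.6·SE·φ(z)/Φ(z).

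**Example, r = 40%, σ = 0.283.** μ = -0.511, SE = 0.1155, z = -0.754, Φ(z) = 0.226. The first-stage shift is -0.154, so the first 6 show 1 - 0.6·exp(-0.154) = 48.6%. The pooled shift is -0.092, so the 10 show 1 - 0.6·exp(-0.092) = 45.3%.

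| True reduction | σ | P(extend) | First 6 | Pooled 10 |
|---|---|---|---|---|
| 40% | 0.2 | 14% | 47.3% | 44.5% |
| 40% | 0.283 | 23% | 48.6% | 45.3% |
| 40% | 0.424 | 31% | 50.8% | 46.7% |
| 45% | 0.2 | 50% | 48.5% | 47.1% |
| 45% | 0.283 | 50% | 49.8% | 48.0% |
| 45% | 0.424 | 50% | 52.1% | 49.4% |

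Simulating 400,000 arms gives the same pooled values to within 0.1 point.

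**Sensitivity.** With σ = 0.60, to allow for between-patient spread, the pooled values are 48.5% (true 40%) and 51.1% (true 45%). If two equally effective lower doses compete and the better is extended, they are 45.4% and 47.0% for a true 40% at σ = 0.283 and 0.424.

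**Other visits.** With equal SDs, the log-scale shift is multiplied by the correlation with week 12, which the documents do not give. At a correlation of 0.5 the example shift becomes -0.046, and the pooled figure is 1 - 0.6·exp(-0.046) = 42.7%.

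**Extension patients alone (n = 4).** With a true 45%, the expected 95% interval on the log scale is ±3.182·σ/√4. That is about 14% to 65% at σ = 0.283, and about -8% to 72% at σ = 0.424.

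**Effect of the switcher rule.** Nothing readable exempts extension patients from the week-12 dose decision. If those below 45% are moved to groups 4 and 5 for the whole study, the same truncation formula with σ in place of SE applies to each patient. With a true 40%, those remaining would show about 52%, 55% and 60% at σ = 0.2, 0.283 and 0.424.

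**Randomised-only contrast with 10 mg/kg.** At σ = 0.283 the SE is 0.283·√(1/6 + 1/3) = 0.200 for 6 against 3, and 0.283·√(1/10 + 1/3) = 0.186 for 10 against 3. Leaving out the extension patients costs about 7% in SE. The selection shift, however, returns from 60% to 100% of its first-stage size.

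**The case against.** Several points on the other side stand.

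- **Pooling is explicit only in the dose-time-response model.** Elsewhere it follows from the lack of a separate group. The Part C summaries also move switchers out, so the arm reported there is not simply 6 plus 4. The figures above describe a plain week-12 mean of all patients by starting dose, not the fitted curve.
- **The trigger is not spelled out.** Protocol 3.2.2 does not say that 45% refers to an arm mean, and the Protocol synopsis words it around the individual patient and adds tolerability.
- **The extension is optional and Part C is exploratory.** The by-arm tumour volume analysis is descriptive and the ANCOVA only may be run.
- **Text is redacted.** The extension sentence runs into blacked-out text in Protocol 3.2.2 and SAP 2.4, and SAP section 4 is not readable. A rule could sit there.
- **The separation can be made from planned data.** Protocol 5.5.1 reserves numbers 5150-5158 for the extension, and tumour volumes are listed.

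A reader might also infer three stronger claims that the documents do not support. The first is that the choice of lower dose rests on the pooled estimate; the dose is identified before the extension starts. The second is that the planned dose contrasts carry the full week-12 bias. The ANCOVA and the Bayesian comparison are at week 4, and the latter already includes 10 mg/kg patients from Parts A and B, so it was never a purely randomised contrast. The third is that restricting contrasts to randomised patients cures the problem; it removes the mixing but leaves the larger first-stage bias.

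**Conclusion.** The point holds as a reporting weakness. On the readable text, extension patients have no group of their own, and the model that describes dose response counts them with the patients who triggered the extension. For a true reduction of 40 to 45%, the pooled week-12 mean overstates the dose by about 2 to 7 points (47.1 - 45 = 2.1; 46.7 - 40 = 6.7). At σ of 0.283 or more, a dose truly at 40% is on average reported at or above the 45% criterion.

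This rests on an arm-mean trigger, normal log ratios and an SD of 0.2 to 0.424, none of which the plan states for Part C. It applies only if the extension is used, and it is smaller at week 4 and at 8 weeks after the last dose. It is a low-severity point with a cheap remedy.

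**What to change.** 1. Flag the extension patients in the SAP. Report their week-12 reduction, with an interval, beside the first-stage patients of that arm and the pooled arm.
2. For this table, keep every patient in the assigned starting dose through week 12. Do not apply the whole-study switcher groups of SAP 7.1, which would bias even the extension column upward.
3. Label the pooled estimate descriptive, state that the arm was selected on its own result, and do not call it confirmation.
4. Show the dose contrast in randomised Part C patients as a sensitivity analysis only. Note that it removes the mixing with non-randomised patients but not the selection bias, which is larger in the first 6 alone.
5. Reconcile the two descriptions of how extension patients enter the arm (Protocol 3.2.2 and 5.2.3), and state whether the 45% trigger is an arm mean.

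The cost is a short SAP paragraph, one extra column and one sensitivity analysis, with no new data. The drawback is precision: about 4 patients give a wide interval, so the separate column guards against over-reading the pooled figure and cannot confirm efficacy by itself.

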3.3 Rationale for dose/regimen, duration of treatment (Parts A and B and C)

For this first study in patients the dose of 10 mg/kg of MCS110 has been selected as the dose that had initially been identified as the highest tolerated single dose Corporate Confidential Information

In addition, a single dose of 10 mg/kg demonstrated pharmacodynamic effects suggesting target suppression up to 42 days, a 40% reduction in monocyte counts, and 80% reduction in bone resorption marker CTX-1 for at least 28 days.

MCS110 is administered by i.v. infusion, which is appropriate as the tumor is highly vascularized. By using the highest dose tolerated, we expect to maximize exposure of drug within the tumor, thus giving patients the best chance for a clinical benefit if there is one. Corporate Confidential Information

Therefore, patients

included in Part A of the proposed study are carefully monitored and appropriate dose adjustment to lower the dose is included in the protocol Corporate Confidential Information

In addition, all other potential adverse events will also be carefully monitored. There is no BMI limit for the patients to allow also obese patients to participate and potentially benefit from the study. As a monoclonal antibody, MCS110 is expected to largely distribute into blood and extra-cellular fluid spaces and then is expected to enter the highly vascularized tumor. In Part A no dose cap was applied in order to not underdose patients with a body weight higher than 100 kg and maintain sufficient exposure at the target site for 28 days.

The follow-up period is planned to be 4 weeks, which is within the general time frame between diagnosis of PVNS and surgery. Corporate Confidential Information

Corporate Confidential Information

3.3.2 Rationale for treatment of adolescent patients (Part C)

PVNS has been reported to occur also in patients younger than 18 years old (Baroni et al 2010; Eckhardt and Hernandez 2004). A high medical need for treatment of PVNS and GCTTS in adolescent patients (12 to 17 years of age) has been identified by the study investigators. Those young patients with PVNS and GCTTS cannot undergo a surgery without worsening the function of their joint or they already have had multiple recurrences of the tumor. Medical treatment with MCS110 is expected to reduce the tumor volume and keep the disease under control or facilitate surgery or eliminate the tumor. Tumor tissue and vascularity is not considered to be different in adolescent patients compared to adult patients.

Novartis	Confidential	Page 80
Amended Protocol Version v07 (Clean)		Protocol No. CMCS110X2201

The exposure in patients with lower body weight has been modeled and is slightly lower with the same dose compared to a 70 kg patient, but this is not expected to have a pronounced effect on safety and efficacy: A simulation was run, considering the 1-hr iv infusion time of 10 mg/kg MCS110, every 4 weeks to patients with body weight of 20 kg (younger than 12 years old), 40 kg (12yrs old) and 70 kg (standard adult) (Figure 3-8). A standard allometric scaling of BWT^0.75 for clearance and BWT for volume of distribution are used, where BWT=body weight in Kg. The simulated typical concentration-time course shows at the same dose per body weight (here 10 mg/kg) that the exposure is slightly lower in children than in adults but would be largely overlapping with those in adults, when variability was taken into consideration.

From the safety point of view it is not likely to see more exposure related adverse events in children than in adults unless children are more sensitive to drug exposure, which is not corporate Confidential Information

Based on

the known effects with antiresorptive agents on bone in children (Glorieux et al 1998; Land et al 2006), it is likely that MCS110 can be administered without serious consequences to an adolescent population for a limited period of time (6 months), and that the effects should be fully reversible after withdrawal of the compound.

From the efficacy point of view, if the exposure is at the plateau of exposure-response in adults, likely the dose would be efficacious enough in this group of children. That is, the difference in exposure might not be large enough to cause a difference in efficacy. This is consistent with most of the other drugs dosed in adolescent patients as compared to adult patients.

Confidential

Corporate Confidential Information

3.4 Rationale for choice of comparator

In Part A and first dose Part B, placebo is used as a comparator to obtain confirmation that during the natural course of the disease the tumor volume changes are very small in 4 weeks. It also allows to estimate or calculate the variability of the tumor volume analysis method by MRI, as this method has not been used or reported before for the quantitative measurement of PVNS tumors.

In Part B, the first dose will be compared to placebo (in a 2 MCS110:1placebo ratio) to continue to increase confidence in the original result from Part A, and to increase experience with change in PVNS tumor volume by MRI over a 4-week period. Repeat MRI measures of PVNS tumor volume have not been published in the literature. Patients who are assigned to placebo arm for the first dose in Part B will receive active drug MCS110 4 weeks later, then every 4 weeks up to a total of 6 doses.

Sufficient data on placebo were collected in Part A and B to get an estimation of the variability of the MRI assessment of tumor volume reduction. In Part C no placebo will be administered.

There will not be any active comparator, as there is no approved drug available today to treat PVNS.

3.5 Risk / Benefit for this study

Potential safety risks associated with MCS110 administration are based on data from Corporate Confidential Information

patients with prostate cancer and bone metastasis, data collected in the single dose Part A and multiple dose Part B of this study, on non-clinical findings with MCS110, and on a recent report on another antibody to M-CSF, Pfizer's PD-0360.

Confidential

Corporate Confidential Information

PVNS and GCTTS patients are generally, apart from their synovitis, healthy young to middle-aged adults. These diseases can occur also in children and adolescents and a high medical need for treatment of PVNS in adolescent patients (12-17 years of age) has been identified.

